18. DATA ANALYSIS PLAN

Aim 1: For the quantitative measures, we will calculate descriptive statistics including the mean number of subjects screened and enrolled per week, percentage of eligible subjects, percentage of eligible subjects enrolled, percentage of subjects completing the intervention and follow-up assessments, and mean ratings on the CSQ-8 items. We will use the Framework Method to analyze the qualitative data from the semi-structured interviews conducted during the follow-up assessment.

Aim 2: In order to obtain a preliminary estimate of the efficacy of the intervention, we will calculate the proportion of subjects who schedule professional treatment within one-month after receiving CBT-TS for Deaf Individuals. We will also use the standardized response mean (SRM) effect size to assess clinically significant change in our treatment-seeking indices: perceptions of treatment (i.e., attitudes toward treatment, subjective norms, and perceived behavioral control), and intention to seek treatment. The SRM represents the ratio of the mean change to the standard deviation of that change and is a form of Cohen's effect size index useful for indicating responsivity to an intervention. The SRM takes into account variability in change over time and is thus more conservative than scores using the standard deviation of the baseline score.

Aim 3: We will use the data from the semi-structured interviews conducted during the follow-up assessment, the quantitative ratings from the CSQ-8, data from the treatment utilization survey about reasons for seeking or not seeking treatment and barriers encountered when attempting to seek treatment, descriptive statistics from the clinical outcome data (e.g., perceptions about treatment, intention to seek treatment, and symptom severity), and recruitment and retention data to inform the refinement of the CBT-TS intervention to enhance its usefulness for Deaf individuals.

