1. PURPOSE OF STUDY

The purpose of the current study is to assess the acceptability and feasibility of a Zoom-based intervention, Cognitive Behavioral Therapy for Treatment Seeking (CBT-TS) to improve professional treatment-seeking among Deaf¹ adults with mental health and/or alcohol use problems. This study is a Stage 1A intervention refinement study (Onken et al., 2014) consisting of a single-arm open pilot trial that will recruit 45 Deaf subjects, aged 18 years or older, with significant symptoms of alcohol use disorder (AUD), post-traumatic stress disorder (PTSD), depression, anxiety, and/or insomnia, who are not currently engaged in treatment. Subjects will be recruited online from across the United States (U.S.) for this remote study. All subjects will complete a baseline assessment of their behavioral health symptoms, perceptions towards treatment, and intent to seek treatment prior to engaging in the CBT-TS intervention. The primary clinical outcome, assessed at one-month follow-up, will be whether subjects scheduled professional treatment. Secondary outcomes include changes in subjects' perceptions towards treatment and intentions to seek treatment. During the one-month follow-up assessment (i.e., at the completion of their participation in the study) subjects will also complete a client satisfaction survey and a semi-structured interview with open-ended questions to provide feedback about the CBT-TS intervention. All study activities will be conducted via Zoom. The specific aims include the following:

Aim 1: Assess the acceptability and feasibility of CBT-TS for Deaf Individuals using recruitment and retention data and qualitative and quantitative subject feedback.

Aim 2: Generate a preliminary estimate of the effect size for CBT-TS for Deaf Individuals using one-month follow-up assessments to assess changes in subjects' utilization of professional treatment services, perceptions of treatment, and intentions to seek treatment.

Aim 3: Refine CBT-TS for Deaf individuals intervention using qualitative and quantitative data from the study to enhance the acceptability and potential effectiveness of CBT-TS for Deaf individuals.

[figure not shown]

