All subjects will be offered an optional second session with the interventionist. The second session will consist of a 60-minute appointment focused on providing practical assistance to identify available treatment options in the subject's area, scheduling treatment sessions, and problem-solving barriers to treatment (e.g., accommodations). Subjects will be informed that the second session must be scheduled within three weeks of completing the first session. The interventionist will immediately offer to schedule a second session at the end of the first intervention session. If subjects do not immediately schedule a second session, study personnel will check in with subjects 10 days after their first intervention session to see if they would like to schedule a second session. If three weeks pass without completing the second session, subjects will proceed with the follow-up assessment at the one-month mark after their first intervention session. If a second session is scheduled, subjects will be contacted for the follow-up assessment one month after completing their second intervention session. The intervention sessions will be video recorded on Zoom and stored on Box.com, a password-protected secure server hosted at URMC.

Follow-up Assessment: One month after their last intervention session, study personnel will contact the subjects to schedule a follow-up assessment session on Zoom. The follow-up assessment will follow the same general procedures as the screening and baseline assessments. During the follow-up assessment, study personnel will re-administer the behavioral health measures and the D-PASS from the baseline assessment, along with a validated treatment utilization survey which will assess subjects' use of 12 treatment services, their reasons for seeking or not seeking treatment, and any barriers they experienced through a series of structured questions.

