15. SUBJECT WITHDRAWALS

Subjects will be advised during the consent process that they have the right to withdraw from the study at any time without penalty. If a subject chooses to withdraw from the study the data collected up until their withdrawal will be used for data analyses. Subjects may be removed from the study if they experience significant distress during the screening and baseline assessments or the intervention session. Withdrawn and removed subjects will be replaced.

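### Does Section 18 need a written denominator and an unknown-status rule for the scheduling proportion, given that subjects who leave are replaced?

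*Combined protocol and SAP*

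**What the plan says.** Section 1 fixes the outcome and its timing: "The primary clinical outcome, assessed at one-month follow-up, will be whether subjects scheduled professional treatment". Section 9 gives the instrument at that visit, where the behavioral health measures and D-PASS are repeated "along with a validated treatment utilization survey which will assess" use of services. The CSQ-8 and the interview are taken at the same visit. Section 9 also states that every subject completes the first intervention session, and it offers an optional second one: "The second session will consist of a 60-minute appointment focused on providing practical assistance to identify available treatment options".

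Section 18, Aim 2, reads: "we will calculate the proportion of subjects who schedule professional treatment within one-month after receiving CBT-TS for Deaf Individuals". Aim 1 lists, among its descriptive statistics, "percentage of subjects completing the intervention and follow-up assessments".

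Section 15 allows removal as well as withdrawal: "Subjects may be removed from the study if they experience significant distress during the screening and baseline assessments or the intervention session". It then says: "Withdrawn and removed subjects will be replaced". For a subject who chooses to withdraw, "the data collected up until their withdrawal will be used for data analyses".

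Section 17 (Missing Data) has reasons for missing data recorded, tabulated, reported and used in judging feasibility.

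**The concern.** A subject can receive CBT-TS, leave before the one-month visit (possibly after distress in the session itself) and be replaced. That person has no CSQ-8 and no utilization survey. If the analyst divides by those followed up, the person drops out of the scheduling proportion. If replaced subjects were also left out of the completion percentages, the loss would not show anywhere.

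Aim 1 judges acceptability and feasibility partly on retention and satisfaction, and Aim 2 supplies the preliminary estimate for a later randomized trial. People who leave after treatment bear on both. From the same data an analyst could report 18/45, 18/50 or 23/50, and nothing in Section 18 says which. The direction of any bias is unknown.

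**Working it through.** **Is there a planned figure to reproduce?** No. Section 5 sets 45 subjects, supported only by the accrual forecast in Section 7. No power, precision target, expected proportion or loss rate is given. The counts and losses below are therefore assumptions, chosen to show a range.

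**Notation.** N = treated subjects, c = those followed up, m = N − c = treated with unknown status, x = followed-up subjects who scheduled.

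- Figure among those followed: x/c
- Lower bound over all treated (unknown = not scheduled): x/N
- Upper bound over all treated (unknown = scheduled): (x + m)/N
- Gap between bounds: (x + m)/N − x/N = m/N, the unknown share, whatever x is

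**With replacement until 45 are followed; x = 18, c = 45.** Among those followed, 18/45 = 40.0%, exact (Clopper-Pearson) 95% interval 25.7% to 55.7%, width 30.0 points.

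| Unknown / treated | Lower bound (95% CI) | Upper bound (95% CI) | Gap m/N |
|---|---|---|---|
| 3 / 48 | 18/48 = 37.5% (24–53%) | 21/48 = 43.8% (29–59%) | 6.3 points |
| 5 / 50 | 18/50 = 36.0% (23–51%) | 23/50 = 46.0% (32–61%) | 10.0 points |
| 12 / 57 | 18/57 = 31.6% (20–45%) | 30/57 = 52.6% (39–66%) | 21.1 points |

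The figure among those followed sits between the bounds. It lies 40.0 − 37.5 = 2.5 points above the lower one in the first row, 4.0 in the second and 8.4 in the third.

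**Without replacement, 45 treated.** With 3 unknown and 17 of 42 scheduling: 17/42 = 40.5%, bounds 17/45 = 37.8% and 20/45 = 44.4%. With 9 unknown and 18 of 36 scheduling: 18/36 = 50.0%, bounds 18/45 = 40.0% and 27/45 = 60.0%, a gap of 20.0 points. At about 20% unknown, replacement neither narrows nor materially widens the gap (21.1 against 20.0 points).

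**When would the gap match the sampling uncertainty?** The gap equals the 30-point interval width only when about 30% of treated subjects are unknown (14 of 45 gives 31.1 points).

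**The replacement rows lean high.** They assume that every lost subject had been treated and was replaced. Section 15 also covers removal at screening or baseline; those subjects were never treated and cannot enter a treated denominator. Section 15 does not say that someone who simply misses follow-up counts as withdrawn.

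**Can a reader recover the bounds from what is planned?** Yes, if withdrawn, removed and replaced subjects stay in the base of the completion percentages. The lower bound is the followed-up proportion times c/N, where c/N is follow-up completion divided by intervention completion, both Aim 1 statistics. In the first row, 0.400 × 45/48 = 0.375, and adding 1 − 45/48 = 0.0625 gives the upper bound 0.4375.

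**The case for a change.** The best case for a change is that the safeguards surround the gap without closing it. Keeping data up to withdrawal supplies no CSQ-8 or survey for someone who left before the visit. Tabulating reasons for missingness is not a rule for counting unknowns. Session 2 may reveal scheduling, but it is optional and not designated as a source for the outcome. The retention sentence covers subjects who choose to withdraw and does not mention those removed. Fixing the rule before outcomes are seen would cost a few sentences.

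All of that is correct on the text. What it shows is missing detail, not a stated rule that gives a wrong answer. The Aim 2 phrase about receiving CBT-TS, read with the statement that every subject completes session 1, already points to treated subjects. A completion percentage is informative only if non-completers are in its base, so the plain reading keeps leavers in. That the CSQ-8 describes those who reached follow-up is evident from when it is given.

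The larger remedies gain little. Offering the CSQ-8 at withdrawal adds a procedure for people who are leaving, perhaps in distress, and its scores would not be comparable with the one-month scores. Counting unknown as not scheduled in the main figure is one convention among several. Distress is already collected as an adverse event, and reasons for missing data already feed the feasibility assessment.

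Accrual does not help the argument either. At 3 to 4 a month, 45 subjects take 45/4 = 11.25 to 45/3 = 15 months, so the slower rate passes 12 months with no replacement at all.

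**Conclusion.** No change to the plan follows. Section 18 does leave out how a treated subject with unknown scheduling status counts. Section 15 leaves open whether loss to follow-up triggers replacement, and whether removed subjects' data are kept. A competent analyst fills these gaps at reporting: show the proportion over all treated beside the one among those followed, give both bounds with exact intervals, keep withdrawn, removed and replaced subjects in the completion percentages, and state the number analysed for the CSQ-8 and the standardized response mean. None of this needs data beyond what is already collected.

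The size equals the unknown share: about 6 points at 3 of 48 and 10 at 5 of 50, against an interval about 30 points wide. At 12 of 57 it is 21 points and no longer small, but a loss of that order would show in the completion percentages. The conclusion rests on the plain reading that those percentages keep leavers in their base, and on the study being a descriptive single-arm Stage 1A pilot with no hypothesis test and no go/no-go threshold. In a trial whose decision turned on this proportion, the rule would need to be written down.

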9. STUDY PROCEDURES

Screening Procedures: Recruitment materials will direct individuals to contact the research team via email or video phone to schedule a screening assessment with study personnel on Zoom. We will use procedures for screening that were successful in the PI's postdoctoral pilot study conducted at URMC. During the screening assessment, study personnel will briefly review the overall study goals and then explain the screening procedures to interested subjects. Study personnel will obtain verbal consent from interested subjects prior to proceeding with the screening assessment. This verbal consent will be documented in REDCap.

Subjects will be screened for eligibility using a (1) brief demographic survey, (2) several behavioral health measures including: the 10-item Alcohol Use Disorders Identification Test (AUDIT) to screen for AUD, 4-items from the National Survey of Drug Use and Health (NSDUH; Center for Behavioral Health Statistics and Quality, 2015) to determine if alcohol use within the past 30 days exceeds the limits for low-risk drinking adopted by NIAAA, the Patient Health Questionnaire-9 (PHQ-9) to screen for symptoms of depression, the Generalized Anxiety Disorder 7-item Scale (GAD-7) to screen for symptoms of anxiety, the PTSD Checklist for DSM-5 (PCL-5) to screen for symptoms of PTSD, and the Insomnia Severity Index (ISI) to screen for symptoms of sleep disturbance, and (3) screening items on the Alcohol Use Disorders and Associated Disabilities Interview (AUDADIS) to determine if there is any history of or current engagement in professional alcohol or mental health treatment.

The screening will begin with the demographics survey and then proceed to the behavioral health measures if the subject is eligible. The behavioral health measures will be administered to subjects in the order listed (see Sources of Research Materials below) until the subject screens positive on one of the measures. If the subject screens positive on one of the behavioral health measures, they will skip to the treatment engagement screening questions. If the subject does not screen positive on any of the behavioral health measures,

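### Aim 2 promises an estimate of change in treatment utilization and the follow-up survey collects use of services, but Section 18 analyses only scheduling

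*Combined protocol and SAP*

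**What the plan says.** Section 1 states that Aim 2 will use the one-month follow-up to "assess changes in subjects' utilization of professional treatment services, perceptions of treatment, and intentions to seek treatment". The same section fixes the clinical endpoint: "The primary clinical outcome, assessed at one-month follow-up, will be whether subjects scheduled professional treatment".

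Section 9 (Follow-up Assessment) adds a validated treatment utilization survey covering "use of 12 treatment services", together with reasons for seeking or not seeking care and barriers met. No baseline administration of this survey is described. At screening, interview items are used "to determine if there is any history of or current engagement in professional alcohol or mental health treatment", and Section 6 requires that subjects have no current behavioral health treatment.

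Section 9 also offers everyone an optional second session. Its content includes "scheduling treatment sessions, and problem-solving barriers to treatment". Follow-up is set one month after the last session taken.

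Section 18 (Aim 2) then specifies two things: "we will calculate the proportion of subjects who schedule professional treatment within one-month after receiving CBT-TS for Deaf Individuals", and a standardized response mean for "clinically significant change in our treatment-seeking indices: perceptions of treatment" and for intention to seek treatment. The utilization survey is named again only under Aim 3, and only for its items on reasons and barriers.

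**The concern.** Aim 2 names three quantities and Section 18 provides for two of them. The third, utilization, is replaced by scheduling without comment. The two are not the same: Section 11 says that subjects who decide to seek treatment may not be able to get it, because of real barriers in the Deaf community.

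Scheduling is also close to the content of the intervention. In the second session the interventionist gives practical help with booking appointments, so for those who attend it the endpoint is partly a process measure.

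Section 12 presents the results as preliminary evidence of efficacy on the way to a randomized trial. If the plan is followed as written, that evidence would be silent on whether anyone reached care, although the data to say so will have been collected.

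**Working it through.** The plan gives no target rate, interval or sample-size derivation for this outcome, so there is no figure to reproduce. The check compares the sections and then works out the observation windows.

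**1. Promise, data and analysis for each component of Aim 2**

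| Component (Section 1) | Data at follow-up (Section 9) | Analysis (Section 18, Aim 2) |
|---|---|---|
| Utilization of services | Survey of 12 services | None; the proportion scheduling is given instead |
| Perceptions of treatment | D-PASS, also at baseline | Standardized response mean |
| Intentions to seek treatment | Re-administered baseline measures | Standardized response mean |

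Aim 3 lists some clinical outcome data for descriptive summary, by way of example. Use of services is not among the examples.

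**2. Can change in use be read from follow-up data alone?** Largely yes. Section 6 excludes current behavioral health treatment, so current use at entry is close to zero by design and use at follow-up approximates new use. Two limits remain:
- The documents do not list the 12 services, so it cannot be confirmed that the screening items cover all of them.
- Eligibility is judged at screening, before the baseline visit and session 1, so a service could be started in between.

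The date on which the reported use began settles both.

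**3. Observation windows** (inputs from Section 9)
- No second session: follow-up falls one month after session 1, about 4 weeks.
- Second session at the three-week limit: 3 weeks + about 4 weeks = about 7 weeks after session 1.
- Difference: up to about 3 weeks.
- In a window fixed at one month from session 1, a subject who takes the second session at three weeks has only about 4 − 3 = 1 week left after it.

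Section 18 does not say whether its one month runs from session 1 or from the last session.

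**4. Dependence of scheduling on second-session uptake (assumed rates)**

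Overall proportion = q × s2 + (1 − q) × s1, where q is uptake, s2 the scheduling rate in takers and s1 the rate in others. With s1 = 30% and s2 = 60% to 90%:
- q = 25%: 0.25 × 0.60 + 0.75 × 0.30 = 37.5%, up to 0.25 × 0.90 + 0.75 × 0.30 = 45%.
- q = 75%: 0.75 × 0.60 + 0.25 × 0.30 = 52.5%, up to 0.75 × 0.90 + 0.25 × 0.30 = 75%.

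None of these rates comes from the documents. They show only that the endpoint would move with uptake if takers schedule more often.

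**5. Precision of the added outcome at n = 45 (assumed counts, exact Clopper-Pearson 95% CI)**
- 9/45 = 20%: 9.6% to 34.6%
- 14/45 = 31%: 18.2% to 46.6%
- 19/45 = 42%: 27.7% to 57.8%
- 24/45 = 53%: 37.9% to 68.3%

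The intervals are about 25 to 30 percentage points wide, enough for a descriptive pilot estimate and no more.

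**The case against.** The strongest reply is that scheduling is the intended measure of utilization. It is named as the clinical outcome in Sections 1, 4 and 18, and help with booking is a deliberate part of the package in a single-arm Stage 1A pilot. The result will be labelled as scheduling and does not claim that anyone reached care. Attendance within one month also depends on waiting lists. All of this stands as a reason to keep scheduling primary. It does not explain why a component named in Aim 2, with its own survey, has no analysis.

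A reader might infer more than the documents support:
- *That change in use cannot be computed.* The eligibility rule of no current treatment undercuts this. What is unconfirmed is only whether the screen covers all 12 services.
- *That the scheduling proportion overstates use by some number of points.* The documents give neither rate, and a proportion labelled as scheduling does not misstate use.
- *That delivering the second session produces the outcome.* The session is optional, it offers assistance, and barriers to access remain.
- *That the survey must be redesigned with scheduling and dates for each service.* Three fields for each of 12 services would be 36 fields added to a validated instrument whose items the documents do not show. It may already hold what is needed.

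**Conclusion.** The point holds as a gap between aim and analysis. One of the three components of Aim 2 is promised and collected but not estimated, and the sole behavioural endpoint is an act that the optional second session assists. This does not invalidate scheduling as the primary clinical outcome, and it does not show that scheduling and use will differ in this sample; their difference is unknown until both are reported.

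The conclusion rests on reading utilization in Aim 2 as use of services, which matches the survey's description. Treating use at follow-up as new use rests on the no-current-treatment rule and on screening items that broadly cover the surveyed services. Because there are few data to add and the gap concerns a stated aim, the change should be made.

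**What to change.** Keep scheduling as the primary clinical outcome and add the following to Section 18, Aim 2:

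- **Secondary descriptive outcome.** The proportion of subjects who used at least one of the 12 services after session 1 and by follow-up, with its denominator and an exact 95% CI.
- **Cross-table.** Scheduled (yes/no) by used (yes/no), which also shows any use without a scheduled appointment.
- **Counting window.** State when it starts and ends, and use the same length for everyone. For example, report use within one month of session 1 alongside use by the follow-up visit. The first compares like with like but leaves late second-session takers little time; the second has the unequal windows shown above.
- **One survey item, only if not already captured.** Whether the first reported use came after session 1, and its date.
- **Second-session uptake.** Any split is descriptive only, because takers select themselves.

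The cost is a short addition to the analysis text, a little extra tabulation and at most one item in a survey already administered. The downside is that waiting lists will hold down attendance within a month, so a low use proportion should be read with that in mind. This is a further reason to keep it secondary.

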5. SUBJECT POPULATION

Subjects will be Deaf adults in the United States with clinically significant symptoms of AUD, PTSD, depression, and/or anxiety, who are not currently engaged in treatment, and whose primary method of communication is ASL or Pidgin Signed English (PSE).

Number: Forty-five subjects will be enrolled in the study.

Gender and Age: Subjects will be 18 years of age and older. Subjects will include all genders.

Race and Ethnic Origin: Based on pilot data, we expect that approximately 73% of the population will be White, 10% will be Black or African American, 6% will be Asian or Pacific Islander, 1 % will be American Indian or Alaskan Native, 10% will be Multiracial, and 13% will be Hispanic or Latinx.

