12. POTENTIAL BENEFITS TO SUBJECTS

Subjects may not receive any direct benefits from participating in this study. Potential benefits to subjects include the opportunity to reflect on their mental health and alcohol use, their beliefs about treatment, and any perceived barriers to treatment in a structured intervention session with a Deaf counselor. In addition, subjects will be provided a list of resources for seeking mental health and/or substance use treatment, as well as practical support in identifying available treatment options, scheduling treatment sessions, and problem-solving barriers to treatment (e.g., accommodations). This support may directly connect subjects with professional treatment for their symptoms. Finally, Deaf individuals are often not consulted for their opinions about services rendered within their own community. Therefore, by being asked for input on future interventions and services for Deaf people, Subjects may experience increased feelings of empowerment and self-efficacy. Given the minimal risks associated with the proposed research and the potential gains both to the individual and Deaf individuals more broadly, the benefits appear to outweigh the risks.

Importance of the Knowledge to be Gained: There is an urgent need to identify interventions that may increase treatment-seeking among Deaf individuals with behavioral health disorders in order to begin addressing current health disparities. If shown effective, CBT-TS may be a promising intervention that could be disseminated within the Deaf community. Results will provide the necessary preliminary data to refine CBT-TS for Deaf individuals and proceed to a randomized controlled trial (RCT) by collecting evidence of the acceptability of the intervention, feasibility of the protocol, and preliminary evidence of the intervention's efficacy.

The proposed study will also provide a reproducible method for adapting evidence-based treatments and provide guidance on how to successfully conduct RCTs within the Deaf community. As such, this work will inform investigators across disciplines and, therefore, has the potential to improve multiple facets of Deaf people's health and wellness across the nation.

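### Section 18 calls the standardized response mean conservative and uses it to assess clinically significant change; neither holds in general

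*Combined protocol and SAP*

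**What the plan says.** Aim 2 in Section 1 is to "Generate a preliminary estimate of the effect size for CBT-TS for Deaf Individuals using one-month follow-up assessments". The same section ranks the outcomes: scheduling professional treatment is the primary clinical outcome, and "Secondary outcomes include changes in subjects' perceptions towards treatment and intentions to seek treatment".

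For those secondary outcomes (attitudes, subjective norms, perceived behavioral control, intention), Section 18 plans the "standardized response mean (SRM) effect size to assess clinically significant change in our treatment-seeking indices". It gives the definition: "The SRM represents the ratio of the mean change to the standard deviation of that change". It then offers two reasons for the choice. One is that the index indicates responsivity to an intervention. The other is that it allows for variability in change and so "is thus more conservative than scores using the standard deviation of the baseline score".

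No condition is attached to that second reason. No other effect size, confidence interval, benchmark or scale-unit threshold is named for these indices.

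**The concern.** Two statements go further than the SRM can support.

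- **Conservative.** Dividing by the SD of change can give a smaller or a larger number than dividing by the baseline SD. Which one depends on the pre-post correlation and on the ratio of the two SDs. The plan presents the direction as a fixed property of the index.
- **Clinically significant change.** The SRM is a group-level ratio of mean change to its variability. It carries no scale units and does not show how many subjects changed by an amount that matters.

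The SRM is the only effect size planned for the secondary outcomes, and Section 12 says the results are to supply preliminary data for moving to a randomized trial. A reader told that the figure is conservative may treat it as a lower-end value when it could be the larger of the two indices.

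**Working it through.** The documents state no number on this point, so there is no figure to reproduce. The check is algebra from the plan's own definition, with assumed ranges for what the documents do not give.

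**Inputs from the documents**

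- SRM = mean change / SD of change (Section 18).
- Paired scores: at the one-month follow-up, "study personnel will re-administer the behavioral health measures and the D-PASS from the baseline assessment" (Section 9).
- Sample size: "Forty-five subjects will be enrolled in the study" (Section 5).

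**Assumed:** the pre-post correlation r; the ratio k = follow-up SD / baseline SD; normal change scores; 80% follow-up in one scenario.

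**Step 1: ratio of the two indices.** With baseline SD s0 and follow-up SD k × s0,

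SD of change = s0 × sqrt(1 + k² − 2rk), so

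SRM / baseline-SD effect = 1 / sqrt(1 + k² − 2rk).

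The SRM is the smaller index only if 1 + k² − 2rk > 1, that is, r < k/2.

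| k | crossover r = k/2 | r = 0.3 | r = 0.5 | r = 0.7 | r = 0.8 |
|---|---|---|---|---|---|
| 0.8 | 0.40 | 0.93 | 1.09 | 1.39 | 1.67 |
| 1.0 | 0.50 | 0.85 | 1.00 | 1.29 | 1.58 |
| 1.2 | 0.60 | 0.76 | 0.90 | 1.15 | 1.39 |
| 1.5 | 0.75 | 0.65 | 0.76 | 0.93 | 1.08 |

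Example: k = 1.0 and r = 0.7 give 1 / sqrt(2 − 1.4) = 1 / 0.775 = 1.29. The plan's sentence is true in 7 of the 16 cells, a tie in 1 and false in 8. These counts describe the chosen grid and are not probabilities.

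**Step 2: simulation at the planned size.** n = 45, bivariate normal, equal SDs, true baseline-SD effect 0.5, 20,000 runs. The SRM exceeded the baseline-SD effect in absolute size in 9% of runs at r = 0.3, 50% at r = 0.5 and 97% at r = 0.7. This agrees with the crossover at 0.5.

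**Step 3: what one SRM value can mean.** Take SRM = 0.50 and equal SDs, with changes measured in baseline SDs. Then SD of change = sqrt(2(1 − r)) and mean change = 0.5 × SD of change. As an illustrative yardstick only, the share improving by more than half a baseline SD is 1 − Φ((0.5 − mean change) / SD of change).

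| r | SD of change | mean change | share improving by more than 0.5 SD |
|---|---|---|---|
| 0.3 | 1.183 | 0.59 | 53% |
| 0.7 | 0.775 | 0.39 | 44% |
| 0.8 | 0.632 | 0.32 | 39% |

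The SRM is identical in all three rows.

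**Step 4: precision.** For an SRM of 0.50, the exact noncentral-t 95% interval is 0.19 to 0.81 with all 45 subjects paired, and 0.15 to 0.84 with 36 (0.80 × 45). Large-sample check at n = 45: SE = sqrt(1/45 + 0.50²/90) = 0.158, and 0.50 ± 1.96 × 0.158 gives 0.19 to 0.81.

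**The case against.** The strongest reply is that little depends on the sentence. The SRM is defined correctly, and responsivity is an independent reason to use it. No test, benchmark, sample size or decision rule rests on it, and the primary proportion does not involve it. Section 12 does not say that the SRM will size the later trial. The direction here is unknown, and the sentence may turn out true for these scales. The phrase about clinical significance could be loose wording for meaningful change, since no cut-off or responder claim is planned.

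It can also be said that Aim 3 already plans descriptive statistics for perceptions and intention. Those would ordinarily give means and SDs at both times. If everything is computed on the same paired subjects, a reader could then work out the baseline-SD effect and, with the SRM, usually the correlation as well. The missing confidence interval is partly a separate matter, because it applies equally to the primary proportion.

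Most of this stands as a limit on consequence: the SRM can stay, and the harm is one of interpretation. It does not rescue the text. An unknown direction is itself the reason not to assert one. The Aim 3 descriptives are meant for refining the intervention; they do not commit to a baseline-SD effect or an interval for Aim 2. With no anchor anywhere for these indices, the stated use of the SRM has no support even on a generous reading.

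**Conclusion.** The concern holds. The claim that the SRM is more conservative is wrong as a general statement: it is true only when r < k/2. Over the assumed range (k from 0.8 to 1.5, r from 0.3 to 0.8) the SRM runs from 0.65 to 1.67 times the baseline-SD effect. Which side of 1 this trial falls on cannot be known from the documents. The SRM alone also cannot assess clinically significant change, since one value is compatible with clearly different amounts of change.

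The algebra needs no assumption beyond the plan's definition. The sizes rest on the assumed r and k, and the shares also on normality, equal SDs and the half-SD yardstick. The effect is confined to how the secondary Aim 2 estimates are read and carried forward. It should be fixed because the plan credits its only secondary effect size with properties it does not have.

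**What to change.** In Section 18, Aim 2:

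- Delete the sentence that calls the SRM more conservative.
- State the purpose of the SRM as estimating the size of pre-post change, in place of assessing clinically significant change.
- Keep the SRM. For each index, also report the mean change in scale units and the change standardised by the baseline SD. Give all three with 95% confidence intervals.
- Report both SDs, the observed pre-post correlation and the number of subjects with paired data.
- Do not describe the SRM as a conservative estimate when planning the randomized trial.

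The wording changes are the minimum correction. The added reporting lets a reader see which index is larger and how precise each is. The cost is two or three sentences of text and a little more analysis of scores already collected at baseline and follow-up. The baseline-SD effect may come out smaller or larger than the SRM, and the plan should accept either.
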